### Quality control

Electronic forms will be used and our database will be checked for appropriateness by the study team. All data will be visually inspected. For exploratory measures, if distributional assumptions are not met (e.g., normality of residuals), transformations or nonparametric methods will be used. Outliers will be closely examined to determine if they are erroneous; if they are valid, sensitivity analyses (with and without outliers) will be used. Hypothesis testing will use  $\alpha=0.10$  (two-tailed). The study team will work closely with [name] and his biostatistics team at ICTR.

### Missing data

Every effort will be made to facilitate participants' completion of questionnaires and provision of data from wearable devices. However, some missing data are inevitable. The magnitude and the reasons for missing data will be recorded and tabulated according to treatment group. If a large proportion of data is missing we will conduct sensitivity analyses using appropriate statistical methods (e.g., maximum likelihood, multiple imputations). If the estimates are similar to the ones obtained from the simpler analysis of only complete cases, we will report the complete-case analysis results.

REDCap allows data entry forms to facilitate completion of all measures. The reasons for missing data will be tabulated. Under the missing at random (MAR) assumption, multiple imputation will be used to obtain unbiased estimates of key statistics. If data are suspected to be missing not at random (MNAR), we will perform a sensitivity analysis such as pattern mixture models. Should these procedures impact the hypothesis tests, we will report all study outcomes both with and without sensitivity analysis.

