Aim 1 assesses the feasibility of time-restricted eating over 12 weeks. We will note how many people we can screen; how many we can approach; how many are eligible; how many consent; and what percentage provide evaluable data at baseline and 12 weeks. Using data from myCircadianClock, we will extract how many days the participants ate within a 10-h window and the average length of the eating window at baseline, week 6, and week 12. We will consider a participant "adherent" if they ate within the 10-h window at least 80% of days. This goal is based on prior TRE studies. In regard to retention, it is hypothesized that at least 80% (24 out of 30) of those who provide baseline data also provide data at 12 weeks; this goal is based on colleagues' prior behavioral intervention studies with supportive care outcomes.

Aim 2 aims to provide estimates of efficacy comparing time-restricted eating vs. control on fatigue. Linear mixed models (LMMs) for longitudinal data will be used to assess the intervention effect on continuous outcomes (e.g., fatigue) accounting for correlations between the repeated measures. Generalized Linear Mixed Model (GLMM) analyses will be conducted to assess the effect of the intervention on count outcomes. The fixed effects included in the models will be treatment group (TRE versus control), time (baseline, 6 and 12 weeks), group-by-time interaction term and relevant covariates. Random effects will include individual patients. The hypotheses will be tested by evaluating the interaction term of group and time (i.e., 12 weeks). The results of the analyses together with the mean and SD of FACIT-F values as well as change scores will be used in planning future RCTs. All hypothesis testing will be at the two-sided level of 0.05. Following the intent-to-treat principle, all participants will be analyzed as randomized, regardless of their adherence with the intervention.

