**2 \* Describe procedures for orderly termination:**  
Upon completion of data collection and return of the actigraph, each participant will be thanked for their participation in the study and compensated for their time.

If a participant withdraws (or is withdrawn) before the end of the study, they will be paid for the time they spent providing data and the study team will not contact the person anymore. A 10-20% withdraw rate is built into the study design and recruitment goal, so there should not be a need to replace participants who withdraw before completing the study.

**3 \* Describe procedures that will be followed when subjects withdraw from the research, including partial withdrawal from procedures with continued data collection:**  
If a participant wishes to withdraw from the study, we will ask if the participant would like to continue participation in some but not all of the research activities. If they would like to participate in only some of the research activities, we will note which ones and the participant will not be formally withdrawn from the study. If they wish to withdraw completely, a written withdrawal request is required and should be sent to the PI (email preferred). The written request for withdrawal will be included in the participant's study record as documentation of the reason for removing a participant from the study. If a participant makes a verbal request and does not provide a written request, the verbal request will be documented by the study team member who receives the request and added to the participant's study record. Data that have been collected thus far will be analyzed.

ID: VIEW4E1B5251F800  
Name: v2\_Withdrawal of Participants

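### When much data is missing, the missing-data rule reports complete cases if estimates look similar, instead of always reporting the mixed model on all observed scores

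*Combined protocol and SAP*

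**What the plan says.** Sample Size and Data Analysis, item 2, fixes the Aim 2 method: "Linear mixed models (LMMs) for longitudinal data will be used to assess the intervention effect on continuous outcomes". Time has three levels (baseline, week 6, week 12), and the hypothesis rests on the group-by-time term at week 12. The same paragraph gives the use of the results: "the mean and SD of FACIT-F values as well as change scores will be used in planning future RCTs".

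The Missing data section adds three further statements.

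- A trigger and a set of methods: "If a large proportion of data is missing we will conduct sensitivity analyses using appropriate statistical methods (e.g., maximum likelihood, multiple imputations".
- A reporting rule for that situation: "If the estimates are similar to the ones obtained from the simpler analysis of only complete cases, we will report the complete-case analysis results".
- In its second paragraph, under missing at random: "multiple imputation will be used to obtain unbiased estimates of key statistics". Pattern-mixture models are added if data are suspected to be missing not at random, followed by a disclosure clause: "Should these procedures impact the hypothesis tests, we will report all study outcomes both with and without sensitivity analysis".

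Withdrawal of Participants, item 3, foresees partial participation: "If they would like to participate in only some of the research activities, we will note which ones". Such a participant is not formally withdrawn.

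**The concern.** The Aim 2 section chooses an analysis that uses every observed score. The Missing data section treats maximum likelihood, the usual way to fit such a model, as a check on a complete-case analysis, and prefers the complete-case result when the two agree. Three terms that decide the outcome are undefined: *large proportion*, *similar* and *complete cases*. Agreement can be judged only after both estimates are known. The second paragraph then calls for multiple imputation without placing it above or below the other two.

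Two analysts who follow the plan could therefore report different main estimates from the same data. The analysis that the rule prefers drops the partial records that the withdrawal section expects. It also needs a stronger assumption: dropout may not depend on the week 6 score, whereas a likelihood fit to all scores allows that where week 6 is observed. What is at stake is the estimate and its precision, because these feed the design of later trials.

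**Working it through.** **Retention range.** Item 1 of the sample size section first recruits 30 with 10–20% attrition: 30 × 0.90 = 27 and 30 × 0.80 = 24 (25.5 at 15%), which reproduces its figure of about 25 evaluable. It now recruits 50 for about 25, and 25/50 = 50%. Withdrawal of Participants still states 10–20%, which would give 40–45 of 50. I therefore use 50%, 80% and 90% retention, meaning the share with a week 12 score, as assumptions.

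**Other inputs.** The prior single-arm study (Justification, Objective, & Research Design, item 3) reports a fatigue subscale change of 5.3, SD 8.1, effect size 0.55. If the effect size was scaled by the baseline SD, that SD is 5.3/0.55 = 9.64, and the correlation is 1 − 8.1²/(2 × 9.64²) = 0.65. Assumed: 25 randomised per arm; correlations (weeks 0–6 / 6–12 / 0–12) of 0.65 throughout, 0.5 throughout, or 0.65/0.65/0.5; true effect 0; half of dropouts have week 6.

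**Precision.** With retention r, the complete-case standard error of the week 12 contrast is √[4σ²(1 − ρ₀,₁₂)/(25r)]. For r = 0.5 and ρ = 0.65 this is √(4 × 92.86 × 0.35/12.5) = 3.22. For all observed data, the per-arm information on the three visit means is 25 Σ wₚ Vₚ⁻¹. The sum runs over the patterns {0, 6, 12}, {0, 6} and {0}, with weights r, (1 − r)/2 and (1 − r)/2. If C is the inverse of that information, SE² = 2(C₁₁ + C₃₃ − 2C₁₃).

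| Correlations | r = 0.5: all data v complete case | Ratio at 0.5 | Ratio at 0.8 | Ratio at 0.9 |
|---|---|---|---|---|
| 0.65 throughout | 3.01 v 3.22 | 1.07 | 1.03 | 1.01 |
| 0.5 throughout | 3.55 v 3.85 | 1.09 | 1.03 | 1.02 |
| 0.65/0.65/0.5 | 3.48 v 3.85 | 1.11 | 1.04 | 1.02 |

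If both analyses adjust for baseline, the penalty at 50% falls to 2–4%. A separate simulation with a random-intercept mixed model and random dropout (600 trials, about half without week 12) gave mean standard errors of 3.04 and 3.28, a ratio of 1.08.

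**Effect of the undefined term *complete cases*.** Suppose that 10% of those randomised miss only week 6. If *complete cases* means all three visits, these people are dropped although they have the endpoint. The standard error is then 20–24%, 10–11% and 7–8% larger at 50%, 80% and 90% retention.

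**Bias.** Suppose that, in one arm only, retention depends on the week 0–6 change, with an odds ratio of 1.65–2.7 per SD. Always reporting complete cases would give a large-sample bias of about 0.9–2.4 points at 50%, 0.4–1.0 at 80% and 0.2–0.5 at 90%. It is about 0 if both arms drop out alike. The plan does not always report complete cases, so the relevant quantity is the bias that the rule adds to an unstructured-covariance likelihood fit (simulated, 25 per arm):

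| *Similar* means within | Complete case chosen, r = 0.5 | Added bias, r = 0.5 | Complete case chosen, r = 0.8 | Added bias, r = 0.8 |
|---|---|---|---|---|
| 1 point | 31–52% | 0.05–0.11 | 64–87% | 0.10–0.21 |
| 2 points | 57–82% | 0.25–0.49 | 93–99% | 0.22–0.52 |
| 3 points | 77–94% | 0.54–0.84 | 99–100% | 0.25–0.66 |

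The tolerance, which the plan does not give, largely decides which analysis becomes the headline at 50% retention.

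**The case against.** The defence is substantial. The rule acts only when the estimates agree, missingness and its reasons are tabulated by arm, and both sets of results are disclosed if the hypothesis tests are affected. That does limit selective reporting. The added bias is small against the standard error: at 50% retention, 0.11/3.01 is under 4% of a standard error, and the loosest tolerance gives at most 0.84/3.01 = 0.28. All bias figures need outcome-related dropout in one arm, which no section predicts. The trial is a pilot with no power calculation that depends on this choice.

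Likelihood is not a cure either. In the same one-arm scenario at 50% retention its own bias is 0.6–1.6 points if no dropout has a week 6 score.

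These points hold and set the size of the concern. They do not remove it. Similar point estimates can still differ in precision, and the disclosure clause is silent when estimates move but the test verdict does not. Nor does that clause say which result leads.

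Three stronger readings are tempting, and the documents do not support them.

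- A reader might infer that no headline exists in the *similar* branch. The sentence does name one, the complete-case result. What is open is entry to the branch and the ranking against multiple imputation.
- A reader might infer that the mixed model is abandoned for a different model. Complete case may mean the same model fitted to completers. Partial data are lost either way.
- A reader might infer that half of the FACIT-F scores will be missing. In Aim 1, *evaluable* refers to eating-window data from the app, and enrolment is counted at consent, before randomisation. The 25 of 50 makes the branch plausible but does not measure questionnaire loss.

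**Conclusion.** The concern holds at minor to moderate severity. Where much data is missing and estimates are judged similar, the plan reports the analysis that discards partial data and needs the stronger missingness assumption. The judgement has no stated criterion and is made after both estimates are seen. Under the assumptions above, the precision cost ranges from 1–2% at 90% retention to 7–11% at 50%. It is larger if week 6 alone is often missed and all three visits are required. The bias added by the rule is 0.05–0.84 points at 50% retention under one-arm dropout on early change, and about 0 if both arms drop out alike.

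Two further inferences should not be drawn. No inflation of the type I error rate is claimed. The intent-to-treat statements are also not contradicted, because they concern assigned group and adherence rather than handling of missing scores.

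**What to change.** In the Missing data section, delete the sentence that reports complete cases when estimates are similar. State that the headline Aim 2 result is always the week 12 group-by-time contrast from the planned mixed model, fitted by (restricted) maximum likelihood to all observed baseline, week 6 and week 12 scores of everyone randomised. Define *complete cases* as either all three visits or baseline plus week 12. Always report the complete-case and multiple-imputation results as sensitivity analyses, whether or not they agree with the headline. Keep pattern-mixture models as already planned, for suspected missing-not-at-random data. Align the second paragraph so that multiple imputation has this same supporting role.

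This is a cheap improvement. It changes wording only, every method is already named in the plan, and no new data or participants are needed. The downside is slightly more analysis and reporting.

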### Note on adherence/non-compliance

This will be an intent-to-treat analysis, and participants will be analyzed in the group to which they were assigned. It is very possible (even likely) that a few participants in the time-restricted eating group will not change their eating habits (non-compliance), and a few people in the control group will be eager to start time-restricted eating (contamination). We will collect data on eating times from the myCircadianClock app during weeks 0, 6, and 12 for both groups, and emphasize the importance of honesty in data collection. Thus, we will be able to assess associations between the length of the eating window and fatigue in exploratory analyses. It is possible that participants will make drastic changes to their behaviors of the course of the study that are independent of their eating window. People might want to initiate a vegetarian diet, weight loss program, exercise program, etc. While we will ask people to continue their normal behaviors, we cannot control people's behaviors and we will not withdraw participants from the study for implementing health behaviors. Any changes in habits will likely occur regardless of what group they are in; therefore there will be noise in the data but we will still be able to estimate the effects of time-restricted eating vs. an unrestricted eating pattern on our outcomes.

ID: VIEW4E02806052800

Name: v2\_Sample Size and Data Analysis

## Sharing of Results

1 \* Describe whether results (study results or individual subject results, such as results of investigational diagnostic tests, genetic tests, or incidental findings) will be shared with subjects or others (e.g., the subject's primary care physicians) and if so, describe how it will be shared:  
Participants may see their complete individual glucose and/or activity data upon request after they complete the study. We will not share data collected for this study with the participant's clinical care team, but the participant is welcome to share it. We will post the final results of the study on clinicaltrials.gov at the completion of the study and share de-identified aggregate results as part of abstracts and manuscripts.

ID: VIEW4E02808CBD800  
Name: v2\_Sharing of Results

## Research with Medical Devices

You indicated on the "Type of Research" page that your study involves the evaluation of device(s) for safety or effectiveness or use of a HUD.

1 \* List all devices to be used in this study:

Device Name	FDA Approved?	Labeled	IDE Number	IDE Holder
View Actigraph	yes	yes		no
View Continuous glucose monitor	yes	no		no
View Bathroom scale	yes	yes		no

2 \* Attach the device labeling or device manual for the devices being used in this study:

Name	Created	Modified Date
Scale-description.pdf(0.01)	3/16/2022 3:05 PM	3/16/2022 3:05 PM
The MotionWatch User Guide.pdf(0.01)	3/16/2022 3:04 PM	3/16/2022 3:04 PM
CGM-User-manual.pdf(0.01)	3/16/2022 3:04 PM	3/16/2022 3:04 PM

3 \* Are you requesting a nonsignificant device risk determination by the IRB? (Applicable if the FDA has not issued an IDE and the device does not qualify to be IDE exempt.)

Yes  No

4 If yes, please provide the rationale for how the device(s) used in the study meet the following criteria:

- Is NOT intended as an implant, is NOT purported or represented to be for use supporting or sustaining human life, and is NOT for a use of substantial importance in diagnosing, curing, mitigating, or treating disease, or otherwise preventing impairment of human health.
- DOES NOT present a potential for serious risk to the health, safety, or welfare of a subject.

5 \* Do you have a plan regarding access controls for essential and appropriate research personnel?

Yes  No

6 \* Will you have procedures for verifying physical access of the device?

Yes  No

7 \* Will the storage of the study device be in a secure environment and include locks on doors and controlled access?

Yes  No

8 \* Will there be an establishment of equipment control both in to and out of the research site?

Yes  No

9 \* Will there be a development of Security Incident Procedures to report any privacy breaches?

Yes  No

10 If applicable, do you have data backup, storage, and emergency mode procedures?

Yes  No

11 If applicable, will the storage of the device be at the appropriate temperature, with a storage and temperature log?

Yes  No

ID: VIEW4E0514D4C8C00

Name: v2\_Research with Medical Devices

## Psychological/Behavioral/Educational Methods & Procedures

You indicated on the "Type of Research" page that your study involves a psychological/behavioral/educational method or procedure such as a survey, questionnaire, interview, or focus group.

1 \* Select all behavioral methods and procedures which apply to this study:

- Surveys/questionnaires
- Key informant or semi-structured individual interviews
- Focus groups or semi-structured group discussions
- Audio or video recording/photographing
- Educational tests or normal educational practices (education instructional strategies, techniques, curricula, or classroom management methods)
- Individual or group behavioral observations
- Psychosocial or behavioral interventions
- Neuropsychological or psychophysiological testing
- Deception
- Other psychosocial or behavioral procedures

ID: VIEW4E09416F57900  
Name: v2\_Psychological/Behavioral/Educational Methods and Procedures

## Surveys/Questionnaires

You indicated that this study involves surveys and/or questionnaires.

If you uploaded a separate research protocol document in the 'Research Protocol' page, cite the applicable section and page numbers from that document in the answer boxes below.

1 \* List all questionnaires/surveys to be used in the study, including both standardized and non-standardized assessments:

On Study  
 Functional Assessment of Chronic Illness-Fatigue (FACIT-F)  
 Brief Fatigue Inventory (BFI)  
 Symptom Inventory (SI)  
 Positive and Negative Affect Schedule (PANAS)-SF  
 Brief Pain Inventory (BPI)  
 Insomnia Severity Index (ISI)  
 Global Physical Activity Questionnaire (GPAQ)  
 Multidimensional Assessment of Interceptive Awareness (MAIA)-2

2 \* Upload a copy of all questionnaires/surveys:

Name	Created	Modified Date
BPI.pdf(0.02)	12/21/2021 5:13 PM	4/29/2022 12:39 PM
Symptom-Inventory.pdf(0.01)	2/22/2022 11:41 AM	2/22/2022 11:41 AM
GPAQ.pdf(0.01)	2/22/2022 11:40 AM	2/22/2022 11:40 AM
ISI.pdf(0.01)	2/17/2022 2:44 PM	2/17/2022 2:44 PM
OnStudy.pdf(0.01)	2/17/2022 2:40 PM	2/17/2022 2:40 PM
PANAS.pdf(0.01)	2/17/2022 2:39 PM	2/17/2022 2:39 PM
FACIT-F.pdf(0.01)	12/21/2021 5:14 PM	12/21/2021 5:14 PM
MAIA.pdf(0.01)	12/21/2021 5:14 PM	12/21/2021 5:14 PM
BFI.pdf(0.01)	12/21/2021 5:13 PM	12/21/2021 5:13 PM

3 \* What is the total length of time that each survey is expected to take?

On Study: 3-8 min  
 Functional Assessment of Chronic Illness-Fatigue (FACIT-F): 5-10 min  
 Brief Fatigue Inventory (BFI): 2-4 min  
 Symptom Inventory (SI): 2-4 min  
 Positive and Negative Affect Schedule (PANAS)-SF: 5-10 min  
 Brief Pain Inventory (BPI): 2-5 min  
 Insomnia Severity Index (ISI): 2-5 min  
 Global Physical Activity Questionnaire (GPAQ): 2-8 min  
 Multidimensional Assessment of Interceptive Awareness (MAIA)-2: 3-10 min

4 \* Are any of the questions likely to cause discomfort in participants or cause harm if their confidentiality were breached? (i.e., Illegal activities)

Yes  No

5 \* Do any questions elicit information related to the potential for harm to self or others?

Yes  No

5.1 If Yes, what procedures are in place to assure safety?

These questionnaires contain information that might be distressing or private (e.g., "I am satisfied with family communication about my illness" from the FACIT-F). Participants are able to skip any questions they are not comfortable answering, and they can take a break or stop answering the questionnaires at any time.

We do not ask about illegal activities.

ID: VIEW4E09460F5EC00  
 Name: v2\_Surveys/Questionnaires

## Interviews

You indicated that this study involves key informant or semi-structured individual interviews.

1 \* Are any of the questions likely to cause discomfort in participants or cause harm if their confidentiality were breached? (i.e., Illegal activities)

Yes  No

2 \* Upload a copy of the interview script or guide that will be used to guide the interviews:

Name	Created	Modified Date
Exit-interview-questions.pdf(0.02)	2/22/2022 11:29 AM	3/10/2022 2:08 PM

3 \* What is the individual duration of each interview and what is the entire duration of the interviews?

15-30 minutes for the single interview

4 \* How will the interview responses be recorded and by whom?

A member of the study team will conduct the interview in-person, by phone, or by videoconference. He or she will take notes during the interview, as well as record the interview with an audio-recorder (Only the audio will be recorded, even for interviews conducted via video conference). The recording will later be transcribed into a de-identified file for qualitative and mixed methods data analysis.

5 \* Do any questions elicit information related to the potential for harm to self or others?

Yes  No

